### **2.3.4. Testing for Antibodies to BioRBCs**

On Day 0, plasma samples will be obtained to test subject's naturally occurring anti-BioRBC antibodies. On Day 32-41 and Day 125-150, plasma samples will be obtained from the subjects. These plasmas will be tested for anti-BioRBC antibodies using a commercial sensitive and specific IgG gel card agglutination assay.

The gel card assay is based on RBC agglutination. The gel cards will be used according to the manufacturer's recommendations (MTS Anti-IgG Card, MTS084024, Ortho Clinical Diagnostics, Rochester, NY). Briefly, 50 µL of the target BioRBC-N or unlabeled RBC (at 0.8% hematocrit in

Diluent 2) are prepared from a group O+ convenience donor and layered atop the buffer in gel card microtubes. Test plasma (25 µL) is added to the target BioRBC or RBC in the gel column and incubated at 37°C for 30 min (ID-MTS Incubator MTS9680 (Ortho Clinical Diagnostics, Rochester, NY). Gel cards are subsequently centrifuged at 895 RPM (80-90 RCF) for 10 min (ID-MTS Centrifuge MT515060, Ortho Clinical Diagnostics, Rochester, NY). The presence of BioRBC agglutination is quantified using the manufacturer's gradation-specific definitions of reactivity. Reactivity scores range from 0 (no agglutination) to 4+ (agglutinates are trapped on the surface of the gel bed).

Detailed testing procedures are provided in a separate laboratory standard operating procedure.

### **2.3.5. Treatment Period**

The study consists of two blood transfusions of one day each separated by approximately one month.

### **2.3.6. Investigational Product Storage and Accountability**

The packed RBCs will be stored under standard blood banking conditions (1-6°C) and transferred to HSCLab one day before the transfusion procedure. All aliquots will be sterile and made using a closed system. The HSCLab will label the RBC within 48 hours of receipt. Preparation of the biotin solution and filter sterilization occur immediately before it is added to the autologous red blood cell sample, which will be prepared immediately prior to infusion to research subjects. In no case will the time from preparation of the biotin solution and biotin-labeled autologous red blood cells to research subject infusion exceed an assigned period of 8 hours.

### **2.3.7 Concomitant Medications**

Subjects will be advised to avoid any nutritional supplement containing biotin (Vitamin B7) and to refrain from eating raw eggs 30 days prior to blood donation and throughout the study period. Potential subjects will be requested to bring a list of any over the counter drugs and/or any nutritional or herbal supplements that they may be taking to the initial screening visit. This list will be documented in the research chart and carefully evaluated by the Physician Investigator for potential interactions with biotin. The Physician Investigator will have final decision regarding the acceptability of concomitant medications. Subjects will be requested to contact the research team prior to taking any new medications (including over-the-counter drugs and vitamin or herbal supplement) during their participation in the clinical investigation.

## **2.4 STUDY ENDPOINTS**

### Primary Endpoint:

The primary endpoint is the labeled red blood cell recovery rate over 60-days post transfusion (using data from 2-4 hours, 1 and 2 month) of 35-42 day stored Bio-RBCs from blood donors with specified genetic mutations, compared with control subjects without the specified mutation.

This protocol may evaluate up to eight (8) genetic mutations as independent studies, compared with pooled control groups, as well as a group of subjects on testosterone replacement therapy. The eight genetic mutations that we will evaluate may include sickle cell trait (AS), and single nucleotide polymorphisms (SNPs) in ankyrin 1 (ANK1), glucose-6-phosphate dehydrogenase X-linked (G6PD), piezo-type mechanosensitive ion channel component 1 (PIEZ01), spectrin alpha

(SPTA), extended synaptotagmin-like protein 2 (ESYT2), Myo9b, and SEC14. We may identify additional SNPs as our analysis of the REDS-III GWAS study advances that could replace one of these SNP groups and/or we identify additional non-synonymous SNPs that are associated with susceptibility to hemolysis of stored red blood cells. In addition we will evaluate 15 subjects on testosterone replacement therapy with 20 controls that are gender and race matched that are not on testosterone replacement therapy. Each group will be considered a separate study for statistical purposes. Controls will be selected based on not having any of the SNPs that will be evaluated in these studies.

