**RBC oxidative hemolysis:** Testing for the impact of genetic mutations on RBC susceptibility to oxidative hemolysis is performed by incubating (1.5-h, 37°C) stored and washed RBCs in the presence of 2,2'-azobis-2-methyl-propanimidamide, dihydrochloride (AAPH, 150mmol/L). After incubation, samples are centrifuged (1500x g, 10min, 18°C), and AAPH-induced oxidative hemolysis is determined by: Oxidative hemolysis (%) =  $\frac{Hb_{\text{AAPH}} - Hb_{\text{control}}}{Hb_{\text{total}}} \times 100$ , where  $Hb_{\text{AAPH}}$  corresponds to supernatant cell-free hemoglobin of AAPH-treated RBCs,  $Hb_{\text{control}}$  corresponds to supernatant cell-free hemoglobin of untreated RBCs, and  $Hb_{\text{total}}$  refers to the total amount of hemoglobin of each sample.

**Membrane microvesicle formation:** RBC-derived microvesicles will be quantified by centrifugation and collection of supernatants from stored RBC units. Microvesicles will be quantified and characterized (size) by flow cytometric analysis as described by Donadee and Gladwin.

**Correlation between primary and secondary endpoints:** We will define the associations between the primary endpoint (60-day in vivo survival of transfused Bio-RBCs) and each of those secondary endpoints by regression analysis using Pearson's r.

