## 2.5 STATISTICAL ANALYSIS

### 2.5.1 Sample Size Determination

In healthy volunteers, the mean (SD) of 30 and 60-days RBC biotin recovery rate is 75% (12.5%) and 50% (10%) (calculated from 24-hour 100% recovery value), respectively. For our first study, evaluating patients with the sickle cell trait SNP, we expect SCD trait to reduce 30 and 60-day recovery to 62% and 25%. A sample size of 15 subjects with sickle cell trait (HbAS) and 20 control African American subjects (HbAA; 10 males and 10 females) would provide 84% power to detect a difference of 13% (SD =12.5%) for 30 days and a power of >95% to detect a difference of 25% (SD = 12.5%) for 60 days RBC recovery rate between AS and AA. This sample size has at least 80% power to detect the interaction between time and genetic group as measure of different recovery rate. We will also recruit an additional 20 Caucasian control (HbAA, 10 males and 10 females) to gain power for testing the effect of other RBC mutations identified in our genome-wide association studies of blood donors (NHLBI RBC-Omics). We will use explanatory analysis for the evaluation of post transfusion recovery of RBCs from subjects with rare variants (<10% of the population) due to a projected small number of subjects carrying such mutations. All 40 control subjects will be tested and selected to not have any of the SNPs that we are studying (listed below).

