### 2.5.2 Statistical Analysis

The primary assessment of RBC transfusion efficacy is post transfusion survival. Data from RBC recovery at 2-4 hours, 1 month and 2 months after each transfusion will be evaluated using mixed effect model (with restricted maximum likelihood variance estimator and bootstrapping) to calculate the effect of time, genetic group and their interaction on RBC survival. RBC recovery at each time point will be performed using the equation below.

$$\text{Percent survival (\%)} = \frac{\text{BioRBCs in circulation at } T_y \text{ (} 1 \leq y \leq 120 \text{ days)}}{\text{Baseline BioRBCs in circulation at } T_0 \text{ (20 min following RBC infusion)}} * 100$$

Secondary endpoints: The equation above will be used to define the 2-4hours post transfusion survival of BioRBCs. The other endpoints test for changes in RBC predisposition to hemolysis in cold storage by quantifying the rates of storage, osmotic, mechanical and oxidative hemolysis and the formation of RBC membrane-derived microvesicles. A sample size of 8 samples would detect a 10% difference in our assays' outputs with a power of 85%. We will use commercial software for statistical analyses (STATA version 15.0, StataCorp., College Station, Texas, USA). We will use mixed effect model (with restricted maximum likelihood variance estimator and bootstrapping) to calculate the effect of time, genetic group and their interaction on RBC survival. Normality tests will help to determine the appropriate transformation of outcome data. We will also use nonlinear term of time in these models (if applicable). We will use marginal test (from the primary models) to assess the effect of genetic group on 60-days and 2-4hours RBC survival separately. As a confirmatory analysis, Wilcoxon signed rank test will determine the differences between two groups for 60-days and 2-4 hours survival rate as well. The hypotheses will be tested primarily in old blood. A separate analysis will be performed in fresh blood transfusion as well. All P value <0.05 will be reported as statistically significant.

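### The primary endpoint is defined both as a rate over three time points and as 60-day survival, and no test is named as decisive; the two can disagree, in sign only under particular conditions.

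*Combined protocol and SAP*

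**What the plan says.** Four places in the combined protocol and SAP bear on what is primary.

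- **Section 2.4, Primary Endpoint** (and, without the time points, the Synopsis): "The primary endpoint is the labeled red blood cell recovery rate over 60-days post transfusion (using data from 2-4 hours, 1 and 2 month"), for cells stored 35-42 days, in carriers against controls.
- **Section 2.5.1**: 15 against 20 subjects is said to give "at least 80% power to detect the interaction between time and genetic group as measure of different recovery rate". The same section also gives power for the 30-day and the 60-day level.
- **Section 2.4, correlation paragraph**: "the primary endpoint (60-day in vivo survival of transfused Bio-RBCs").
- **Section 2.5.2**: "The primary assessment of RBC transfusion efficacy is post transfusion survival". The mixed model is used "to calculate the effect of time, genetic group and their interaction on RBC survival". Then: "We will use marginal test (from the primary models) to assess the effect of genetic group on 60-days and 2-4hours RBC survival separately". A rank test repeats the 60-day and 2-4 hour comparisons, and "All P value <0.05 will be reported as statistically significant". No test is named as primary.

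The zero point also varies. The survival equation in Section 2.5.2 divides by a count 20 minutes after infusion. Visit 6 in Section 2.2.2 calls the 2-4 hour sample the baseline. The planning figures in Section 2.5.1 set the 24-hour value to 100%. Section 2.5.2 leaves any transformation of the outcome to normality tests.

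**The concern.** A difference in level at day 60 and a difference in rate of decline are separate hypotheses. Stored cells can be lost soon after infusion, and the plan lists 2-4 hour survival as a secondary endpoint. If carriers lose extra cells early and the survivors then age like control cells, the level at day 60 is lower, but the later decline in percentage points is no steeper and may be flatter.

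The same data could then support a clear 60-day deficit with no rate difference, or, in some settings, a deficit and a slower loss together. With no test named as decisive, the choice could be made after the results are seen, in each of up to nine comparisons (eight genetic groups and the testosterone group).

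**Working it through.** **1. The plan's own power figures.** Inputs from Section 2.5.1: n = 15 and 20, SD 12.5, differences of 13 points (30 days) and 25 points (60 days). Two-sided 0.05 is assumed, since sidedness is not stated.

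- SE = 12.5 × √(1/15 + 1/20) = 4.27
- 30 days: 13/4.27 = 3.04; noncentral t, 33 df: 84.0% (stated 84%)
- 60 days: 25/4.27 = 5.86; 99.99% (stated above 95%)

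Both reproduce. The interaction figure cannot be reproduced exactly because no within-subject correlation is given. For the 30-to-60 day contrast (25 − 13 = 12 points, SD 12.5 at both times), power is 49%, 64%, 78%, 86% and 94% at correlations 0, 0.3, 0.5, 0.6 and 0.7. If everyone starts at exactly 100%, the change to day 60 is the 60-day level, and power exceeds 99%.

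**2. When the two readings differ.** Let R be 2-4 hour recovery as a percentage of T0, and s the 60-day survival relative to 2-4 hours (a = carriers, c = controls). I take the interaction as a linear time slope. With roughly equal spacing (0, 30, 60 days) that slope equals the change from 2-4 hours to day 60, divided by 60.

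- Level difference: L = Ra·sa − Rc·sc
- Change difference: D = Rc(1 − sc) − Ra(1 − sa)
- With L negative, the signs are opposite when Ra/Rc < (1 − sc)/(1 − sa)

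The control figures in Section 2.5.1 give sc = 0.50, so the threshold is 0.50/(1 − sa):

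| Carrier sa | Reversal needs Ra/Rc below |
|---|---|
| 0.50 (normal later ageing) | 1.00 |
| 0.45 | 0.91 |
| 0.40 | 0.83 |
| 0.25 (planned effect) | 0.67 |

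Under the planned effect from a common 100%, L = 25 − 50 = −25 and D = 50 − 75 = −25, so they agree exactly. For a parallel absolute loss D = 0, while L equals the early loss. On the log scale the change difference is ln(sa/sc): zero when sa = sc, and negative when carriers age faster. If the 2-4 hour or 24-hour value is the 100% reference, the early loss drops out and L = D.

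**3. How often, at 15 against 20.** Simulated trials with t tests at two-sided 0.05 and control means 100/75/50. SDs at 30 and 60 days are 12.5 and 10, from Section 2.5.1. The 2-4 hour SD (5) and the correlation (0.5) are assumptions, because the documents give neither.

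| Carrier means | 60-day test, carriers worse | Slope test | Both significant, opposite |
|---|---|---|---|
| 80/60/40 (20% early loss) | about 81% | about 91%, favouring carriers | about 72% |
| 90/67.5/45 (10% early loss) | about 29% | about 38%, favouring carriers | about 1% |
| 85/60/35 (parallel 15 points) | about 99% | about 5% (chance level) | – |

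For the 20% loss I varied the 2-4 h SD (5-10), the 60-day SD (10 or 12.5; Section 2.5.1 uses both) and the correlation (0-0.8). The 60-day test is then significant in 62-81%, the slope test in 43-99%, and both in opposite directions in about 15-80%. For the 10% loss the same grid gives 0-14%; the top needs a 2-4 h SD of 10 with correlation 0.8.

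**4. False positives.** With no group effect, letting either the 60-day or the slope test count gives about 7.5% at the central assumptions, against a nominal 5%. Over the same grid it runs from about 6.5% to 9%.

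**The case against.** - **The conflict is partly one of words.** Section 2.5.1 uses the term for a percentage at a time point: "the mean (SD) of 30 and 60-days RBC biotin recovery rate is 75% (12.5%) and 50% (10%) (calculated from 24-hour 100% recovery value"). The 60-day label in Section 2.4 sits in a correlation paragraph, where Pearson's r needs one number per subject. This has some force, but the interaction sentence in Section 2.5.1 expressly ties a rate difference to time by group, and Section 2.5.2 does not choose.
- **The sign reversal is conditional.** A reader might infer that any early storage loss sets the two readings against each other. The documents do not support that. Reversal needs the untransformed percent scale, a T0 before the loss, and an early deficit large relative to later excess loss. The visit schedule lists no separate 20-minute draw, and two other baselines appear. This objection stands in full.
- **The 2-4 hour test would expose an early loss.** In the 20% scenario it is significant in about 100% of runs. True, but it does not say which test decides the primary claim.
- **A larger false-positive rate, about 11%, might be inferred** by also counting the 2-4 hour test. The Synopsis and Section 2.5.2 place 2-4 hour survival among the secondary endpoints, so that figure should not be used.
- **This is a pilot with an exploratory first aim.** That lowers the stakes. The protocol nevertheless names a primary endpoint, powers it and sets a significance threshold.
- **Choosing the interaction would also be consistent with the text.** Agreed; the recommendation for day 60 rests on practicality.

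**Conclusion.** The concern holds as a contradiction with consequences. The primary endpoint is stated two ways, Section 2.5.2 does not say which test decides, and the hypotheses differ. The result that needs least assumption is the parallel loss: a 15-point deficit is found at day 60 in about 99% of trials (93% if the 60-day SD is 12.5) and appears as an interaction only at the 5% chance rate.

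Opposite signs are possible but not general. For a 20% early loss with normal later ageing, both tests are significant and opposed in about 15-80% of trials; for a 10% loss, in about 1% at the central assumptions. These figures rest on the percent scale, a baseline before the loss, and assumed early losses, 2-4 hour SDs and correlations. They do not apply on the log scale, with the 2-4 hour or 24-hour value as reference, or under the effect planned in Section 2.5.1. The inflation from 5% to about 7.5% per comparison is modest. The 30-day and 60-day power arithmetic is sound.

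**What to change.** In the Synopsis, Section 2.4 (both places) and Section 2.5.2, name one primary quantity and test: the carrier-minus-control difference in 60-day survival of 35-42 day stored cells, from the marginal test already planned. Label the interaction, the 1-month and 2-4 hour differences and the rank test as supportive. Cite the 60-day power in Section 2.5.1 (above 95% for 25 points) as the power of the primary test.

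State one T0 in advance, reconciling 20 minutes (Section 2.5.2), 2-4 hours (Visit 6) and 24 hours (Section 2.5.1), and one outcome scale. Without these, 60-day survival remains undefined.

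The cost is protocol and SAP wording, with no change in sample size. The real downside is that the interaction can no longer be claimed as a primary result.

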#### Secondary Endpoints:

- Define the 1-hour post transfusion survival of fresh or stored Bio-RBCs
- Determine the association between gender and in vitro correlates of the RBC storage lesion and post transfusion recovery of BioRBCs at selected time points (i.e. 2-4 hours, 60 days). The in vitro measurements of stored RBCs test include spontaneous cold storage hemolysis, osmotic hemolysis, mechanical fragility, AAPH-induced oxidative hemolysis, and membrane microvesicle formation. RBC predisposition to hemolysis is quantified as percent hemolysis, which accounts for the levels of RBC-derived free hemoglobin in response to cold storage (5-7 and 35-42 days following donation) or exposure of washed and stored RBCs to osmotic or oxidative stress.

**Storage hemolysis:** quantification of storage hemolysis is based on the equation:

Storage hemolysis (%) =  $\frac{(100-HCT) \times Hb_{\text{supernatant}}}{Hb_{\text{total}}}$ , for which HCT refers to the sample hematocrit (HCT),  $Hb_{\text{supernatant}}$  refers to the levels of free hemoglobin obtained after centrifugation (1500x g, 10min, 18°C) measured in the supernatant, and  $Hb_{\text{total}}$  refers to the total amount of sample hemoglobin before centrifugation.

**Stress hemolysis assays:** For the evaluation of stress-induced hemolysis, stored RBCs are washed (1500x g, 10min, 18°C) three times with phosphate-buffered saline (PBS) to remove plasma and additive solution, and immediately subjected to osmotic or oxidative stress assays.

**RBC osmotic hemolysis:** Osmotic hemolysis is determined by incubating (4h at 22°C) stored and washed RBCs in pink test buffer (a hypotonic Bis-Tris buffer containing 25mmol/L sodium chloride, 70mmol/L Bis-Tris buffer, and 135mmol/L glycerol; pH 6.6) at a final concentration of 1.6%±0.2% after which samples were centrifuged (1500x g, 10min, 18°C), and percent osmotic hemolysis is determined by: Osmotic hemolysis (%) =  $\frac{Hb_{\text{osmotic}}}{Hb_{\text{total}}} \times 100$ , for which  $Hb_{\text{osmotic}}$  corresponds to supernatant cell-free hemoglobin of pink test-treated RBCs and  $Hb_{\text{total}}$  refers to the total amount of hemoglobin of each sample.

**RBC oxidative hemolysis:** Testing for the impact of genetic mutations on RBC susceptibility to oxidative hemolysis is performed by incubating (1.5-h, 37°C) stored and washed RBCs in the presence of 2,2'-azobis-2-methyl-propanimidamide, dihydrochloride (AAPH, 150mmol/L). After incubation, samples are centrifuged (1500x g, 10min, 18°C), and AAPH-induced oxidative hemolysis is determined by: Oxidative hemolysis (%) =  $\frac{Hb_{\text{AAPH}} - Hb_{\text{control}}}{Hb_{\text{total}}} \times 100$ , where  $Hb_{\text{AAPH}}$  corresponds to supernatant cell-free hemoglobin of AAPH-treated RBCs,  $Hb_{\text{control}}$  corresponds to supernatant cell-free hemoglobin of untreated RBCs, and  $Hb_{\text{total}}$  refers to the total amount of hemoglobin of each sample.

**Membrane microvesicle formation:** RBC-derived microvesicles will be quantified by centrifugation and collection of supernatants from stored RBC units. Microvesicles will be quantified and characterized (size) by flow cytometric analysis as described by Donadee and Gladwin.

**Correlation between primary and secondary endpoints:** We will define the associations between the primary endpoint (60-day in vivo survival of transfused Bio-RBCs) and each of those secondary endpoints by regression analysis using Pearson's r.

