## **1.4 SIGNIFICANCE**

The quality of a unit of stored RBC for transfusion, a procedure performed about 12 million times per year in patients, is currently based on levels of storage hemolysis. However, the storage lesion is a singular manifestation of a multitude of injuries that occur during red cell storage. Hemolysis measures alone failed to capture the progressive accumulation of these changes, some of which may affect the ability of transfused red blood cells to traverse the microcirculation. Furthermore, there is limited data on the correlation between *in vitro* measures of hemolysis and post-transfusion survival of stored red blood cells. This project explores the current gaps in understanding the impact of genetic and biologic factors in blood donors on red blood cell storage stability and post transfusion recovery. We also seek to determine whether *in vitro* markers of storage integrity can predict red cell survival in the patient circulation.

Our studies in human and animal models have demonstrated that genetic variability and biological variables such as sex, age, race or iron availability may significantly modulate predisposition to hemolysis under diverse stress conditions including routine cold storage of RBC units, and in hemolytic disease. For example, we have shown that RBCs from male donors (human or mice) exhibit higher susceptibility to hemolysis during storage, and under osmotic, mechanical or oxidative stress. Furthermore, we have demonstrated the effect of donor sex, testosterone or sickle cell trait on RBC storage and post-transfusion recovery in a murine model of transfusion. As members of NHLBI REDS-III and collaborators on the RBC-Omics project, we have further demonstrated in 13,403 informed blood donors that variables such as sex, race, and donation intensity may modulate RBC hemolytic response to cold storage and to osmotic and oxidative stress. Having completed the screening of these donors for hemolytic propensity, we are currently seeking for genes that mediate hemolysis using genome-wide association approach. The biotin method would provide us the unique opportunity to verify whether our *in vitro* correlates of hemolysis or the newly discovered genes may predict RBC recovery *in vivo*.

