This power calculations informs our other planned studies that will compare up to 7 additional single nucleotide polymorphisms (SNPs) patient groups of 15 each, compared with our control groups without the SNPs (n=20 race and gender matched). Successful enrollment of the sickle trait and 7 SNP groups would be 120 total subjects. The eight genetic mutations that we will evaluate may include sickle cell trait (AS), and single nucleotide polymorphisms (SNPs) in ankyrin 1 (ANK1), glucose-6-phosphate dehydrogenase X-linked (G6PD), piezo-type mechanosensitive ion channel component 1 (PIEZ01), spectrin alpha (SPTA), extended synaptotagmin-like protein 2 (ESYT2), Myo9b and SEC14. We may identify additional SNPs as our analysis of the REDS-III GWAS study advances that could replace one of these SNP groups and/or we identify additional non-synonymous SNPs that are associated with susceptibility to hemolysis of stored red blood cells. In addition, we will evaluate 15 subjects on testosterone replacement therapy with 20 controls that are gender and race matched that are not on testosterone replacement therapy.

Each study will be conducted as an independent analysis of 15 subjects with the SNP and 20 race and gender matched subjects without the SNP using power calculations estimated from the SCD trait example above.

**Biotin infusion study:** The study team will target 70 evaluable subjects. The study team will approach 86 subjects with 90% expected to agree to yield 78 subjects who will sign the biotin infusion consent. The study team expects 90% of these subjects to complete the biotin infusion study yielding the target 70 evaluable subjects. The biotin infusion subjects include 20 Whites, 20 African American without sickle cell trait, 15 African Americans with sickle cell trait, and 15 males on testosterone. In addition, 20 subjects with SNPs from the REDS-III RBC-OMICS study will be included for a total of 98 subjects to sign the biotin infusion consent and yield approximately 90 subjects who complete the study.

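### The planned Pearson's r between in vitro markers and 60-day survival has no group term, so a significant value cannot by itself show that a marker predicts survival beyond the carrier-control difference

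*Combined protocol and SAP*

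**What the plan says.** The last paragraph of Section 2.4 is the whole specification of this analysis. It relates the primary endpoint, described there as 60-day in vivo survival, to "each of those secondary endpoints by regression analysis using Pearson's r". It does not say which subjects enter, and it mentions no term for genotype, testosterone therapy, sex or race. Section 2.5.2 puts genetic group into the mixed model for survival but adds nothing for the correlation.

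On the unit of analysis, Section 2.4 states: "Each group will be considered a separate study for statistical purposes". Section 2.5.1 describes each such study as an "independent analysis of 15 subjects with the SNP and 20 race and gender matched subjects without the SNP".

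On purpose, Section 1.4 wants to learn whether "markers of storage integrity can predict red cell survival in the patient circulation", and the Synopsis and Section 1.1 list the correlation as part of the secondary objective. The only threshold is the general rule in Section 2.5.2: "All P value <0.05 will be reported as statistically significant".

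**The concern.** The carriers are not a random sample of donors. The Study Rationale in the Synopsis says the candidate variants were found through their association with more hemolysis under storage, osmotic or oxidative stress, and these are the properties that the in vitro markers measure. Section 2.5.1 also expects sickle-trait carriers to have much lower 60-day recovery. When two groups differ on both axes, a scatter of one axis against the other shows a correlation even if the marker says nothing about survival inside either group.

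The carrier-control difference in survival is already tested by the primary model. A marker correlation that only restates that difference adds no evidence that the marker carries information beyond genotype. At stake is how a significant secondary result may be read.

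**Working it through.** **The plan's own figures.** Section 2.5.1 uses "A sample size of 15 subjects with sickle cell trait (HbAS) and 20 control African American subjects". At 30 days it claims "84% power to detect a difference of 13% (SD =12.5%) for 30 days". Its 60-day claim is power above 95% for a 25-point shift at the same SD. A two-sample t-test at two-sided 0.05 (sidedness is not stated, so this is assumed) has noncentrality (13/12.5)/sqrt(1/15 + 1/20) = 1.04/0.3416 = 3.04 on 33 degrees of freedom. The power is 84.0%. At 60 days the noncentrality is 2.0/0.3416 = 5.86 and power exceeds 99.9%. Both statements reproduce, so these inputs are used below.

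**Inputs**
- Group sizes: 15 carriers and 20 controls (Section 2.5.1).
- Survival shift dY: 25/12.5 = 2.0 SD (Section 2.5.1, sickle trait only).
- Marker shift dX: not in the documents. Assumed range 0 to 2 SD.
- Within-group correlation: set to zero, to isolate what the group difference does alone.
- Distribution: normal within groups with equal SDs (assumed).

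**Correlation produced by the group difference.** With carrier share p = 15/35 and c = p(1 − p) = (15 × 20)/35² = 0.245,

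|r| = c × dX × dY / sqrt[(1 + c × dX²)(1 + c × dY²)].

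For dX = 1 and dY = 2: 0.245 × 2 / sqrt(1.245 × 1.980) = 0.490/1.570 = 0.31. The sign is negative for a hemolysis marker that is higher in carriers. The smallest |r| that reaches P < 0.05 with 35 subjects is 0.334.

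**How often r is significant**, from 20,000 simulated trials per setting, dY = 2.0 SD:

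| Marker shift (SD, assumed) | Absolute r | Unadjusted r significant |
|---|---|---|
| 0 | 0 | 5% |
| 0.5 | 0.17 | 16% |
| 1.0 | 0.31 | 48% |
| 1.5 | 0.42 | 77% |
| 2.0 | 0.50 | 93% |

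The group-adjusted (partial) correlation was significant in 4.6% to 5.5% of trials in every setting tried.

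**Sensitivity**
- Section 2.5.1 also gives an SD of 10 for 60-day recovery in healthy volunteers. The shift is then 2.5 SD, and the rates for marker shifts of 0.5 to 2 SD are 20% to 98%.
- If the survival shift is only 0.25 to 0.5 SD, as it may be for other variants, the rates for marker shifts of 0.5 to 1.5 SD are 5% to 13%.
- The value of r depends on the enrolled mix. With a 1 SD marker shift and a 2 SD survival shift, 15 carriers among 35 give 0.31. If the 70 target infusion subjects were put together and only the 15 with sickle trait differed, the same shifts would give 0.24.

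**Power kept after adjustment.** By Fisher's z with 35 subjects and one covariate, the standard error is 1/sqrt(35 − 1 − 3) = 0.180. For a within-group r of 0.5, z = 0.549/0.180 = 3.06 and power is about 86%. For r of 0.3, z = 0.310/0.180 = 1.72 and power is about 41%.

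**The case against.** Four points on the other side deserve weight.

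- **Pooling.** A reader might infer that r is computed over all genetic groups together. The documents do not say so, and the separate-study wording in Sections 2.4 and 2.5.1 points away from it. This stands. The mixing remains inside each study, however, because each study holds carriers and controls. That r is taken over both is the natural reading of a silent text, not a stated rule.
- **False positives.** A reader might take 16% to 93% as an inflated type I error. In those settings the correlation across the mixed sample is not zero, so the test detects something real. The rates are errors only if the question is association within groups. This stands.
- **The target.** The objectives do not restrict the association to donors of one genotype. A marker that separates low-survival from normal-survival donors is useful in a mixed donor population, and hemolysis may lie on the path from genotype to survival, so that adjusting removes part of the signal. This stands, and it is why the unadjusted r should be kept.
- **Consequence.** A reader might infer that the plan would declare success on this statistic. Section 2.4 only says that associations will be defined, Section 2.1 calls the trial a pilot, and Aim 1 is to explore. No decision rule is attached beyond reporting P < 0.05.

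None of this answers whether a marker informs beyond the group contrast, and the plan has no analysis that would.

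**Conclusion.** The concern holds as a cheap improvement. As written, the plan has an unadjusted correlation with no analysis set and no group term, in studies that each combine two groups expected to differ. A significant r therefore cannot alone support a statement that a marker predicts survival beyond the group difference.

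The size rests on two things. The 2 SD survival shift is the sickle-trait expectation and is not given for any other group. The marker shift is assumed throughout: at zero there is no excess, and with small survival shifts the excess is slight. The primary analysis and the stated power are unaffected.

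**What to change.** In Section 2.4 or 2.5.2:

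1. State which subjects enter each correlation.
2. Beside the unadjusted r, report a regression of 60-day survival on each marker with a genetic (or testosterone-therapy) group term. Add sex and race only where they vary within the study: race is constant in the sickle-trait study, and sex is constant in the testosterone study, where subjects are male and controls are matched.
3. Give the group-adjusted slope or partial correlation with its interval, and check the marker-by-group interaction, since a single common slope is otherwise assumed.
4. Base any claim of prediction within donor groups on the adjusted estimate, and describe the unadjusted r as the association in the enrolled mix.

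This needs plan wording only and uses data already collected. It costs one or a few degrees of freedom. Power with 35 subjects and one covariate is good for a within-group r of 0.5 (about 86%) but not for 0.3 (about 41%), so a non-significant adjusted result should not be read as evidence of no association.
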